hospitalizations, and disease activity of SLE will also be evaluated in all patients at defined visits (see [Table 6-1](#)). Adverse events not collected in this study should be reported in accordance with the laws and regulations for marketed products in the country in which the event occurred.

Primary Endpoints:

Incidence of the following adverse events of special interest (AESI):

- Malignancies (excluding non-melanoma skin cancers)
- Mortality
- Opportunistic infections and other infections of interest ([Appendix 1](#))
- Non-melanoma skin cancers (NMSC)
- Selected serious psychiatric events ([Appendix 2](#))
- Serious infections

Effectiveness Endpoints:

- Organ damage as assessed by SLICC/ACR Damage Index ([Appendix 5](#))
- Concomitant SLE medications including steroids
- Hospitalizations

Sample Size Consideration:

This registry will enroll approximately 3,000 patients, approximately 2,000 receiving or initiating BENLYSTA plus standard of care (BENLYSTA cohort) and 1,000 standard of care only (comparison cohort). Each patient will be followed for 5 years, contributing a total of approximately 7,773 patient years in the BENLYSTA cohort and 3,886 patient years in the comparison cohort, respectively), assuming a 10% annual patient drop-out rate and not accounting for crossover.

The registry will allow the difference in mortality rate in the BENLYSTA cohort and comparison cohort to be established with a 95% CI of +/-0.32 per 100-subject years, based on an estimated mortality rate of 0.68 per 100-subject years in both treatment groups ([Table 1](#)). The estimated mortality rate was based on the mortality rate in the pooled IV primary safety database in SLE subjects derived from 3 randomized, double-blind, IV placebo-controlled trials, referred to as IV SLE Controlled, Repeat Dose (CRD) studies (ie, integrated database of LBSL02 [placebo-controlled treatment phase only], HGS1006-C1056, and HGS1006-C1057) for all subjects (IV belimumab and placebo) adjusted for subject years. The precision of the rates of the AESI are provided in the table below:

Table 1 Precision of differences in AE rates estimated from a total of 7,773 patient years in the BENLYSTA cohort and 3,886 patient years in the comparison cohort, respectively

Adverse Events	Reference Rate¹ (per 100-patient years)	95% Confidence Interval for difference in AE rates² (per 100-patient years)
All deaths	0.68	±0.32
Serious infection	5.80	±0.93
Opportunistic infection	0.136	±0.14

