1.2 BENLYSTA Background Relevant to the Registry

BENLYSTA (belimumab) is a recombinant human IgG1 λ monoclonal antibody that binds to soluble human B-lymphocyte stimulator (BLyS; also known as B cell activating factor belonging to the tumor necrosis factor (TNF) family [BAFF] and TNFSF13B) and inhibits its biological activity (Baker, 2003).

The primary safety population, derived from 3 randomized, double-blind, IV placebo-controlled trials, referred to as IV SLE Controlled, Repeat Dose (CRD) studies, included safety data from the double-blind portion of the two phase 3 studies discussed above (HGS1006-C1056 and HGS1006-C1057) as well as the double-blind portion of a Phase 2 study (LBSL02) in 449 subjects with SLE. A summary of adverse events of special interest in this dataset, the same as that to be evaluated in this registry, is provided in Table 1-1. Additional information is provided in the Package Insert/Summary of Product Characteristics.

Table 1-1 Adverse Events of Special Interest (IV SLE CRD) ¹

	Placebo N = 675	1 mg/kg N = 673	10 mg/kg N = 674
All Cause Mortality			
Deaths	3 (0.4%)	5 (0.7%)	6 (0.9%)
Infections and Infestations			
At least 1 Infection AE	455 (67.4%)	484 (71.9%)	477 (70.8%)
At least 1 serious infection AE	37 (5.5%)	48 (7.1%)	36 (5.3%)
Opportunistic infections	-	1 (0.1%)	2 (0.3%)
Malignancies			
Malignancies (all)	3 (0.4%)	4 (0.6%)	3 (0.4%)
Non-melanoma skin cancers (NMSC)	1 (0.1%)	1 (0.1%)	3 (0.4%)
Malignancies excluding NMSC	2 (0.3%)	3 (0.4%)	-
Hematological malignancies	-	-	-
Psychiatric Disorders			
Psychiatric Disorders (SOC)	84 (12.4%)	108 (16.0%)	107 (15.9%)
Serious	3 (0.4%)	4 (0.6%)	8 (1.2%)
Depression/Self-Injury	34 (5.0%)	44 (6.5%)	41 (6.1%)
Serious	2 (0.3%)	3 (0.4%)	4 (0.6%)
Suicide	-	1 (0.1%)	1 (0.1%)

¹ Final integrated safety data from 3 IV SLE CRD trials: LBSL02, HGS1006-C1056 and HGS1006-C1057.

With respect to mortality, 14 deaths occurred during the double-blind periods of these 3 randomized, placebo-controlled SLE trials: 3 (0.4%) in the placebo group, 5 (0.7%) in the

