8.2 Sample Size Consideration

This registry will enroll approximately 3,000 patients approximately 2,000 receiving or initiating BENLYSTA plus standard of care (BENLYSTA cohort) and 1,000 standard of care only (comparison cohort). Each patient will be followed for 5 years, contributing a total of approximately 7,773 patient years in the BENLYSTA cohort and 3,886 patient years in the

comparison cohort, respectively, assuming a 10% annual patient drop-out rate and not accounting for crossover.

The registry will allow the difference in mortality rate in the BENLYSTA cohort and comparison cohort to be established with a 95% CI of +/-0.30 per 100-subject years, based on an estimated mortality rate of 0.68 per 100-subject years in both treatment groups (Table 8-1). The estimated mortality rate was based on the mortality rate in the pooled IV primary safety database in SLE subjects derived from 3 randomized, double-blind, IV placebo-controlled trials, referred to as IV SLE CRD studies (ie, integrated database of LBSL02 [placebo-controlled treatment phase only], HGS1006-C1056, and HGS1006-C1057) for all subjects (IV belimumab and placebo) adjusted for subject years. The precision of the rates of the AESI are provided in the table below:

Table 8-1 Precision of differences in AE rates estimated from a total of 7773 patient years in the BENLYSTA cohort and 3886 patient years in the comparison cohort, respectively

Adverse Events	Reference Rate¹ (per 100-patient years)	95% Confidence Interval for difference in AE rates² (per 100-patient years)
All Deaths	0.68	±0.32
Serious infection	5.80	±0.93
Opportunistic infection	0.136	±0.14
Malignancy excl. NMSC	0.226	±0.19
NMSC	0.226	±0.19
Serious Psychiatric Events	0.410	±0.25

¹ The reference AE rates were based on the AE rates in the pooled IV primary safety database derived from 3 IV SLE CRD studies (LBSL02, HGS1006-C1056, HGS1006-C1057) and adjusted for subject years.

² Assuming that the AE rates in BENLYSTA and the control groups were the same as the reference rate.

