8.3.2 Analysis of Primary Endpoints

In addition to analyses that consider initial treatment group (BENLYSTA cohort vs. comparison cohort), analyses that specifically account for changes in therapy (in either group) by considering a variety of risk windows will be employed. These analyses will attribute events to BENLYSTA treatment if they occur within the designated risk windows for BENLYSTA exposure and to comparison treatment otherwise. These analyses will allow for a registry patient to contribute person-time to both BENLYSTA treatment, and comparison treatment and as a result, will specifically account for treatment switching to BENLYSTA or from BENLYSTA. Switching between BENLYSTA and comparison treatment will be taken into account in a number of ways in the analysis and will be further defined within the statistical analysis plan. No new analyses for changing between BENLYSTA formulation or stratifying by BENLYSTA formulation are planned. Planned analyses are outlined below; all analyses will be detailed in the statistical analysis plan.

- Analysis by initial treatment group of rate per person years of observation time.
- Analysis by initial treatment group of rate per person years of exposure where BENLYSTA exposure ends 14 weeks (approximately 5 half-lives) after cessation of treatment.
- For serious psychiatric events, BENLYSTA exposure is all time on treatment with BENLYSTA ending 14 weeks (approximately 5 half-lives) after cessation of treatment, with all remaining treatment time attributed to the comparison cohort.
- For serious infections, opportunistic infections and other infections of interest, BENLYSTA exposure is all time on treatment with BENLYSTA ending 6 months after cessation of treatment, with all remaining treatment time attributed to the comparison cohort.
- For NMSC and malignancies excluding NMSC, analysis will be performed where all events will be attributed to BENLYSTA if the patient was ever exposed to BENLYSTA treatment prior to the event and attributed to the comparison cohort otherwise (ie, once exposed, always at risk).
- Mortality will be analyzed applying all the above-mentioned risk windows (eg, 14 weeks, 6 months, and ever-exposed).
- Other risk windows (including risk windows for comparison treatment) may also be assessed and defined in the statistical analysis plan.

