**2.2. Study Objective(s) and Endpoint(s)**

Objectives	Endpoints
Primary	Primary
To evaluate the incidence of selected adverse events of special interest (AESI) over 5 years in adults with active autoantibody-positive systemic lupus erythematosus (SLE) who are treated with or without BENLYSTA	Comparison of incidence rates, over a 5-year period, of listed Adverse Events of Special Interest (AESI) among adult SLE subjects who are exposed or unexposed to BENLYSTA: 
 
1. Malignancies (excluding non-melanoma skin cancers)
 
2. Mortality
 
3. Opportunistic infections (serious and non-serious)*
 
4. Other infections of interest (serious and non-serious)*
 
5. Non-melanoma skin cancers (NMSC)
 
6. Serious psychiatric events
 
7. Serious infections
 

Other	Other
To evaluate selected effectiveness measures in adults with active autoantibody-positive SLE who are treated with or without BENLYSTA	
 
1. Comparison of mean change from baseline in SLICC/ACR Damage Index (SDI) score over a 5-year period in adult SLE subjects who are exposed or unexposed to BENLYSTA
 
2a. Comparison of proportions of subjects with concomitant SLE medication use, including steroids (as defined below), over a 5-year period in adult SLE subjects who are exposed or unexposed to BENLYSTA                             
Over the past six months the daily dose was either:
 
 
i. Always < 7.5 mg/day
 
ii. >= 7.5 mg/day for <= 2 weeks
 
iii. >= 7.5 mg/day for > 2 weeks
 
 
 
2b. Comparison of mean change from baseline in six-month average daily corticosteroid dose (prednisone equivalent, mg/day) assessed over 5-year period in adult SLE subjects who are exposed or unexposed to BENLYSTA
 
3. Comparison of incidence rates, over a 5-year period, of hospitalizations (as shown below) among adults SLE subjects who are exposed or unexposed to BENLYSTA:                             
 
i. All hospitalizations
 
ii. SLE-related hospitalization
 
 
 

Tertiary/Exploratory	Tertiary/Exploratory
NA	NA

\* Computation of rates will be done separately for opportunistic infections and other infections of interest (these were combined as one in the protocol)

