## 2.4. Statistical Hypotheses / Statistical Analyses

The purpose of the study is to evaluate the incidence of AESI over 5 years in adults with SLE being treated with and without BENLYSTA in a real-world setting. No formal statistical hypotheses testing will be conducted since there is no pre-specified hypothesis for any of the study endpoints.

Unless otherwise specified, the following measures will be used:

- Categorical variables will be summarized as the number of subjects and percentages (%) of subjects in each category. Percentages will not include the missing category and will be calculated over the number of subjects with available (non-missing) data.
- Continuous variables will be summarized using the mean, standard deviation (SD), median, first and third quartiles (Q1, Q3), minimum (min), maximum (max).
- Computed percentages will be presented with one decimal place. Percentages equal to 100 will be presented as 100% and no percentage will be presented for zero frequencies. In case of presenting CIs for categorical/qualitative data, exact methods for deriving these intervals will be used in case of descriptive statistics.
- The 95% CI will be computed for rates to contextualize the extent of random error but will not be used for formal statistical hypothesis testing.

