## 5.7. Multiple Comparisons and Multiplicity

No adjustments for multiple comparisons are planned. There will be no formal statistical testing, analyses including comparison of estimates will be descriptive only..

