

- Calculation of an individual's subject-years of follow-up for each exposure strategy is shown in Appendix 2 (Section 9.2).

 
Incidence and event rates will be calculated and reported per 100 subject-years. The 95% CI for the rate will be calculated assuming an exact Poisson distribution method [Stokes, 2012].

Model Checking & Diagnostics

• No model-based statistical analysis will be performed; hence there is no model checking and diagnostics to be conducted.

Results Presentation
Total number of events, number and % of subjects with events, total subject-years at-risk, and total subject-years of follow-up will be reported. In addition, incidence proportion (where applicable), incidence rate, event rate and their 95% CI will be presented. The mock-shell tables showing details of data displays are presented in Appendix 12.
Subgroup Analyses
This analysis may be conducted for each study cohort separately (Current Users and Treatment Initiators; Section 5.6.2) . The list of TLF Data Displays is presented in Appendix 11.
Sensitivity Analyses
This analysis will also be conducted using the 'Evaluable Sensitivity' population. Details of the planned displays are provided in Appendix 11: List of TLF Data Displays.

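### Protocol 8.2 states mortality-difference precision of ±0.30; its own table, the synopsis and the inputs give ±0.32, and the supplied SAP text never states the between-group contrast this refers to

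*Protocol*

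**What the plan says.** **Protocol, precision.** The registry is sized on precision alone. The text of Section 8.2 says it will allow "the difference in mortality rate in the BENLYSTA cohort and comparison cohort to be established with a 95% CI of +/-0.30" per 100 subject-years, assuming 0.68 deaths per 100 subject-years in both groups, and points to Table 8-1. In Table 8-1 the deaths row reads ±0.32. The synopsis has the same sentence with the same rate and person-years, but there the difference is "to be established with a 95% CI of +/-0.32 per 100-subject years", and synopsis Table 1 agrees. Both tables give 0.226 and ±0.19 for malignancy excluding NMSC and for NMSC.

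**Protocol, analysis.** Section 8.3.2 lists rates by group, beginning with "Analysis by initial treatment group of rate per person years of observation time".

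**SAP.** Section 2.2 words the primary endpoint as "Comparison of incidence rates, over a 5-year period, of listed Adverse Events of Special Interest (AESI"). Section 2.4 says "The 95% CI will be computed for rates to contextualize the extent of random error", and Section 5.7 says "analyses including comparison of estimates will be descriptive only". In the results paragraph of Section 7.1.5.1, "incidence proportion (where applicable), incidence rate, event rate and their 95% CI will be presented". Section 7.3.1 names a weighted Poisson regression with stabilized weights as the outcome model. Section 7.3.1.5 then defines only weighted rates for each group, with limits that treat the weighted count as a Poisson count. Tables 24.110, 24.120, 54.010 and 54.020 in Appendix 11 are titled as proportions and rates.

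**The concern.** The ±0.30 contradicts the table it cites and claims more precision than the design gives. Nothing downstream depends on it, but anyone quoting Section 8.2 carries a wrong figure for the one design property the sample size rests on.

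The second matter is an improvement, not a broken promise. The precision is stated for a difference between cohorts, and the SAP calls the endpoint a comparison. Yet the supplied text gives no rate difference or rate ratio, and no variance estimator for the named regression. The weighted analysis is the SAP's only adjustment for confounding. As written it yields two adjusted rates with separate intervals, and readers must build the comparison themselves. Doing so from the weighted totals is nearly harmless if the weights vary little and gives too narrow an interval if they vary more. The spread of the weights is not known in advance.

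**Working it through.** **1. Person-years.** With 10% annual drop-out over 5 years, PY = N × (1 − 0.9⁵)/(−ln 0.9). N = 2,000 gives 7,773.5 and N = 1,000 gives 3,886.75, so the protocol's 7,773 and 3,886 reproduce.

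**2. Half-widths.** For two equal Poisson rates r per 100 PY, half-width = 1.96 × √[r × (1/77.73 + 1/38.86)].

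| Event | Rate | Computed | Tables 1 and 8-1 |
|---|---|---|---|
| Deaths | 0.68 | 0.3175 | ±0.32 |
| Serious infection | 5.80 | 0.927 | ±0.93 |
| Opportunistic infection | 0.136 | 0.142 | ±0.14 |
| Malignancy excl. NMSC; NMSC (each) | 0.226 | 0.183 | ±0.19 |
| Serious psychiatric | 0.410 | 0.247 | ±0.25 |

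The deaths row reproduces the tables, not the Section 8.2 text. The shortfall is (0.3175 − 0.30)/0.3175 = 5.5%. A half-width of 0.30 needs a rate of (0.30/1.96)²/(1/77.73 + 1/38.86) = 0.607. Splitting the same total person-years equally would give 0.2994, which may be where ±0.30 came from, but the documents do not say so.

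**3. Malignancy and NMSC rows.** By the same inversion, ±0.19 needs a rate of about 0.243. The documents do not settle which cell is wrong. Protocol Section 1.2 reports that "14 deaths occurred during the double-blind periods of these 3 randomized, placebo-controlled SLE trials", and Table 1-1 gives 5 malignancies excluding NMSC, 5 NMSC and 3 opportunistic infections. Scaling, 0.68 × 5/14 = 0.243, which fits ±0.19. But 5/0.226 and 3/0.136 (per 100) imply 2,212 and 2,206 PY, which agree with each other, while 14/0.68 implies 2,059 PY.

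**4. Rebuilding a comparison from weighted totals.** This is a simulation on assumptions, because the documents give no weight distribution. It has 3,000 patients at about 2:1, 10% annual drop-out over 5 years and no exposure effect. One normal confounder has log-rate 0.5 per SD and log-odds of exposure 0.3, 0.6 or 0.9 per SD. Stabilized weights come from a logistic propensity score, and their coefficients of variation (CV) are about 0.14, 0.30 and 0.48. There were 6,000 runs for mortality and opportunistic infection and 4,000 for serious infection (Monte Carlo SE about 0.3 to 0.6 points). Variance per arm:
- rebuilt: Σ(w·y)/(Σ w·PY)²
- robust: Σ[w(y − r·PY)]²/(Σ w·PY)²

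Coverage of the nominal 95% interval:

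| Interval | CV 0.14 | CV 0.30 | CV 0.48 |
|---|---|---|---|
| Mortality difference, rebuilt | 94.2% | 91.0% | 86.8% |
| Mortality difference, robust | 95.1% | 94.1% | 92.8% |
| Mortality ratio, robust | 95.5% | 94.7% | 94.5% |
| Serious infection, first events, rebuilt | 94.5% | 93.5% | 88.6% |
| Serious infection, first events, robust | 95.5% | 96.2% | 94.9% |
| Opportunistic infection difference, rebuilt | 93.5% | 91.3% | 86.3% |
| Opportunistic infection difference, robust | 94.1% | 92.9% | 89.8% |
| Opportunistic infection ratio, robust | 96.2% | 95.1% | 92.9% |

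The rebuilt mortality half-width stays at 0.32. The robust one is 0.33, 0.36 and 0.40, close to the empirical 1.96 × SD of 0.330, 0.366 and 0.410. With no confounder effect on mortality, rebuilt coverage is still 94.9%, 93.1% and 90.5%. With recurrent serious infections it is 93.7%, 90.6% and 84.5%, part of which is overdispersion.

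**5. Sparse events.** Expected opportunistic infections are 0.136 × 77.73 = 10.6 and 0.136 × 38.86 = 5.3. At 11 versus 5 the crude rate ratio is 1.10, with exact conditional 95% CI 0.35 to 4.04.

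**The case against.** The ±0.30 is one prose figure, contradicted by the table it cites. By itself it is an editorial correction, and that stands.

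On the contrast, the protocol's objective is to evaluate incidence and its listed analyses are rates by group. Precision for a difference can be read as a sizing device only, and the SAP disclaims hypotheses. So there is no breach. But Section 5.7 excludes tests, not estimates; it speaks of comparing estimates itself.

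Absence is also not fully established. The mock shells are in a separate file, and the figures near Sections 7.3.3 and 7.3.4 and some SAP pages were not available. The named regression could yield a rate ratio. The SAP's reference list includes a paper on intervals for an exposure-adjusted rate difference that no supplied text cites, but other entries are uncited too, so it shows no intent. If the shells already carry a contrast, what remains is to state its method.

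The rebuilt difference interval is not one the SAP specifies, and the weight spreads are assumed. The SAP also inspects weights, truncates extreme ones and stops if balance fails. However, its own weighted exact Poisson interval for the comparison group, simulated under the same mortality assumptions, covers 94.5%, 90.9% and 85.8% at the three spreads. The problem is therefore not confined to the rebuilt interval.

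Two cautions stand in full. The robust interval under-covers for the sparsest events, and crude contrasts in a registry open to confounding can be over-read.

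**Conclusion.** The Section 8.2 figure is wrong as written. On the protocol's own rate and person-years the half-width is 0.3175, so ±0.32. This part is certain and needs no outside assumption. The malignancy and NMSC rows disagree internally by 0.007 per 100 PY, which is minor, and only the source calculation can settle it. Neither error changes sample size or analysis.

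The missing contrast is a worthwhile, inexpensive improvement, subject to the unseen shells and pages. Its importance depends on how much the weights vary. At a CV near 0.14 the shortfall in coverage is about one point; at 0.48 it is about eight points for mortality, under the simulation assumptions above.

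**What to change.** 1. In Protocol Section 8.2, change ±0.30 to ±0.32.
2. Reconcile the malignancy and NMSC rate and half-width in Tables 1 and 8-1 with the source calculation.
3. In SAP 7.3.1.5, report the weighted rate ratio and/or difference from the exposure term of the Poisson regression already named in 7.3.1, with a log subject-years offset and a robust variance. Keep it descriptive, without a test, and give it only where the balance criterion in 7.3.1.2.2 is met.
4. In SAP 7.1.5.1, add the crude contrast, labelled unadjusted, with an exact or small-count interval for sparse events.
5. Show these in Tables 24.110, 24.120, 54.010 and 54.020.

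The cost is one corrected figure, a check of two table rows and a little programming. The crude contrasts need a confounding caveat. The robust weighted intervals will be somewhat wider than ±0.32 for mortality. For the sparsest events they need a caveat of their own: at opportunistic-infection rates and a weight CV of 0.48, simulated coverage is 89.8% for the difference and 92.9% for the ratio.

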
1. Incidence rate will be calculated for each exposure group as follows:
 $\text{Incidence Rate} = \frac{\sum \text{at risk subjects with at least one event}}{\sum \text{subject years at risk}} \times 100$ 
 
- Incidence rate is defined as the number of 'at-risk' subjects experiencing first event (i.e. number of new cases) during the specified follow-up period divided by total subject-years at-risk of that event for all subjects at risk.
 
- Although the categorization of study follow-up time to Benlysta (Exposed) or Non-Benlysta (Unexposed) depends on the exposure assignment strategy (see Appendix 2, Section 9.2.1 for further discussion), the follow-up time included in the subject-years at-risk calculation, for each month xx time period, starts from enrollment date and ends at the earliest of the following: 
 
o First event date
 
o Last contact date (as defined in Section 9.5.3)
 
o Month xx target date (Section 5.3)
 
o Censored date (for While on Initial Exposure strategy; see Section 9.2.1.1)
 
o Data cut-off date
 
 
Additionally, for some exposure strategies (e.g. 'As-Exposed' strategy; see Appendix 2, Section 9.2.1.2), time to treatment switch and risk windows are also considered when categorizing follow-up time into 'Exposed' and 'Unexposed' period.
 
 
- Calculation of an individual's subject-years at-risk for each exposure strategy is shown in Section 9.2.
 
- Subject-years at-risk will be calculated for each event type separately.
 
- Only the first experience of the event (i.e. new cases) or first primary diagnosis (in the case of a malignant event) which occurred during the 'at-risk' period are counted (see Section 9.2.1 for time period considered for each exposure strategy).
 
- For summary of each specific AESI category, subjects experiencing events in multiple AESI categories will be counted in more than 1 AESI category.
 
 
2. Event rate will be computed for each exposure group as follows:
 $\text{Event rate} = \frac{\sum \text{all AESI events}}{\sum \text{subject years of follow-up}} \times 100$ 
 
- Event rate is estimated for potentially recurrent events and represents the average number of events per unit time of follow-up. It is defined as the total number of events experienced by all subjects during the specified study period divided by subject-years of follow-up. The categorization of study follow-up time depends on the exposure strategy (see Appendix 2, Section 9.2.1). The subject-years of follow-up for each month xx time period takes the same definition above for the subject-years at-risk, however, follow-up does not stop at the time of first event.
 
- Additionally, for some exposure strategies (e.g. 'As-Exposed' strategy), time to treatment switch and risk windows are also considered when categorizing follow-up time into exposed and unexposed period (Section 9.2.1.2)
 
- All events experienced during the follow-up period including recurrent events are counted (see Section 9.2.1 for time period considered for each exposure strategy).
 

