## NOTE:

- i. Individual's subject-years at-risk will be calculated for each event type separately and if required for each time period (i.e. for analysis by time period)
- ii. Individual subject-years of follow-up may be required for each time period (i.e. for analysis by time period)

\* Last Contact Date as defined in section 9.5.3

2. While On Initial Exposure analysis approach will be used to analyze all data accrued up to the first treatment switch. Any events and follow-up time accrued after the first exposure switching (switching from Initial Exposure) will be censored (i.e. excluded from analysis) at first exposure switch date (see Section 5.14 for the definition of exposure/medication switching).

A limitation of this analysis approach is potential bias introduced by underreporting of events experienced during the study since data from only a subset of the study period and events collected before the first treatment switch are included in the analysis. The results only present risk of exposure prior to first treatment switch. See Section 9.2.1.2 for details of 'As-Exposed' (Time Varying) approach to address this.

**Programming Hints for derivation of essential variables needed for computation of incidence and events rates (presented in Section 7.1.5.1) under the While On Initial Exposure approach:**

- Compute First Switch Date as:  

$$\text{Baseline Benlysta Medication End Date} + 98 \text{ days (for switching from Benlysta to Non-Benlysta) or}$$

$$\text{First Post-Baseline Benlysta Start Date} - 1 \text{ (for switching from Non-Benlysta to Benlysta)}$$
- Compute individual's subject-years at-risk as:  

$$[(\text{minimum (Event Date, First Switch Date, Last Contact Date}^*) - \text{Study Enrollment Date}) + 1] / 365.25$$

- Compute individual's subject-years of follow-up as:
 
$$\frac{[(\text{minimum}(\text{First Switch Date}, \text{Last Contact Date}^*) - \text{Study Enrollment Date}) + 1]}{365.25}$$
- Consider events experienced up to First Switch Date (if switching from Initial Exposure) or whole study period (if no switch):
 
$$\text{Study Enrollment Date} \leq \text{Event Date} \leq \text{minimum}(\text{First Switch date}-1, \text{Last Contact Date}^*)$$
  - For incidence rate calculation only count new cases (i.e. first onset) of the event experienced during the period
  - For events rate calculation count all the events experienced during the period

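### The ±0.93 precision for serious infection rests on follow-up to drop-out; on the SAP's primary first-event incidence rate the plan's inputs give about ±0.96 to ±0.99

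*Protocol*

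**What the plan says.** Protocol 8.2 sizes the registry by precision. It plans "approximately 2,000 receiving or initiating BENLYSTA plus standard of care (BENLYSTA cohort) and 1,000 standard of care only" patients, and states: "Each patient will be followed for 5 years, contributing a total of approximately 7,773 patient years in the BENLYSTA cohort", with 3,886 in the comparison cohort, "assuming a 10% annual patient drop-out rate and not accounting for crossover". Table 8-1 is titled "Precision of differences in AE rates estimated from a total of 7773 patient years in the BENLYSTA cohort and 3886 patient years" (the second total is for the comparison group). It applies these totals to all six events, with equal rates assumed in both cohorts. Its serious-infection row reads "Serious infection 5.80 ±0.93". Table 1 in the Synopsis repeats the same basis: "Precision of differences in AE rates estimated from a total of 7,773 patient years in the BENLYSTA cohort and 3,886 patient years".

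SAP 2.2 names the comparison of incidence rates as the primary endpoint. SAP 7.1.5.1 defines the incidence rate as the number of at-risk subjects with a first event "divided by total subject-years at-risk of that event for all subjects at risk". The clock stops at the earliest of several dates, one of which is the date of the first event. The ITT programming rule in SAP 9.2.1.1 does the same. SAP 7.1.5.1 also defines a second measure, the event rate, which counts recurrent events and keeps the clock running after the first one.

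Neither document says which of the two measures the precision tables describe, or whether 5.80 is a first-event or an all-event rate.

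**The concern.** For a rare event the two denominators are nearly equal. Serious infection is not rare: at 5.80 per 100 patient-years over 5 years, enough patients leave the risk set at their first infection to shorten the time at risk visibly. A half-width computed on full follow-up is then too narrow for the first-event incidence rate.

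The plan has no hypothesis test, so these tables are its only stated justification for the registry's size. Serious infection is the most frequent event in them, and Protocol 1.3 names it as a particular safety question. A reader who takes ±0.93 as the precision of the primary measure would be somewhat too optimistic about the excess rate the registry can exclude.

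**Working it through.** **Inputs.** From Protocol 8.2 and Table 8-1: 2,000 and 1,000 patients, 5 years, 10% annual drop-out, 5.80 per 100 patient-years in both cohorts, 95% interval. From Protocol Table 1-1: counts of subjects with each event in the three source trials. From SAP 7.1.5.1: time at risk ends at the first event. Hazards are taken as constant.

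**Formulas.** With total exit hazard H, person-years = n(1 − e^(−5H))/H. Half-width = 1.96 × √[r(1/PY₁ + 1/PY₂)], with r the rate per person-year.

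**1. The plan's own figure.** The drop-out hazard is h = −ln(0.9) = 0.10536.
- Person-years per patient: (1 − 0.59049)/0.10536 = 3.887, so 7,773.5 and 3,886.8. These match the protocol without any term for the event itself.
- Half-width: 1.96 × √[0.058 × (1/7,773 + 1/3,886)] = 0.00927, or ±0.93 per 100. Reproduced.

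**2. First-event time at risk, 5.80 read as a first-event rate.** H = 0.10536 + 0.058 = 0.16336.
- Person-years: 2,000 × (1 − e^(−0.8168))/0.16336 = 6,833, and 3,417 for the comparison cohort, about 12% less.
- Expected first events: 0.058 × 6,833 = 396 and 0.058 × 3,417 = 198. The table's denominators imply 451 and 225 events.
- Half-width: 1.96 × √[0.058 × (1/6,833 + 1/3,417)] = 0.00989, or ±0.99. This is 0.989/0.927 = 1.07 times the stated figure.
- A simulation of 4,000 registries with exponential infection and drop-out times gave 1.96 × SD = 0.985 and a mean half-width of 0.989.

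**3. 5.80 read as an all-event rate.** The source subject-years are not stated, but can be inferred by dividing Table 1-1 counts by reference rates:
- malignancy excluding NMSC: 5/0.00226 = 2,212
- opportunistic infection: 3/0.00136 = 2,206
- serious depression/self-injury: 9/0.0041 = 2,195

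On an assumed 2,210 subject-years, 5.80 corresponds to 0.058 × 2,210 = 128 infections, but Table 1-1 has 37 + 48 + 36 = 121 subjects with at least one. The first-event rate would be about 121/2,210 = 0.0548. Then H = 0.16016, person-years are 6,881 and 3,440, and the half-width is 0.958, or about ±0.96.

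This inference is not firm. A shorter at-risk base of 121/0.058 = 2,086 subject-years would also give 5.80, and the 14 deaths give 14/0.0068 = 2,059.

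**4. Other rows, full follow-up against first-event time at risk.**

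| Event | Full follow-up | First-event |
|---|---|---|
| Deaths | 0.318 | 0.320 |
| Opportunistic infection | 0.142 | 0.142 |
| Malignancy excl. NMSC; NMSC | 0.183 | 0.184 |
| Psychiatric | 0.247 | 0.248 |

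None changes at two decimals.

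**The case against.** The strongest reply is that the table is right for the rate it describes. Its title speaks of rates over patient-years, Protocol 8.3.2 lists first an analysis over all observed person-time, and SAP 7.1.5.1 plans an event rate on full follow-up. SAP 7.3.3 even labels the weighted event rate as primary alongside the weighted incidence rate. For an event rate of 5.80, ±0.93 is the correct Poisson half-width. This stands, so a reader should not infer that Table 8-1 contains an arithmetic error. It does not make ±0.93 the precision of the incidence rate, which SAP 2.2 names as the primary endpoint. Even for the event rate, the figure ignores clustering of repeat infections within patients.

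It is also fair to say that little depends on the number. SAP 2.4 and 5.7 exclude formal testing, and SAP 7.1.5.1 specifies exact Poisson intervals for each group's rate. No interval for the difference is specified, and every reported interval will come from observed events and time. That limits the consequence to the stated planning precision.

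Three stronger readings are tempting and not supported:
- **±1.00.** Adding deaths at 0.68 per 100 as a further exit gives 6,734 and 3,367 person-years and 0.996. The protocol does not say whether the 10% drop-out already includes deaths.
- **A loss of power.** With no hypothesis test in the plan, there is no power to lose.
- **A known further loss for While On Initial Exposure.** SAP 5.1 also places that approach under primary analysis, and SAP 9.2.1.1 says: "Any events and follow-up time accrued after the first exposure switching (switching from Initial Exposure) will be censored". Its precision will be lower if patients switch. The documents give no switching rate, so the size cannot be derived, and the protocol already discloses that crossover is left out.

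**Conclusion.** The point holds in a limited form. The only precision the plan states for serious infection does not describe its primary incidence rate. On that measure the plan's own inputs give about ±0.96 to ±0.99 instead of ±0.93, an interval roughly 3% to 7% wider. The upper figure assumes that 5.80 is a first-event rate. The lower one assumes that it is an all-event rate with a first-event rate near 5.5, which depends on an inferred source of about 2,210 subject-years. Both assume constant hazards, equal rates in the cohorts, and drop-out and first infection as the only exits before 5 years. The effect is confined to serious infection. It is a mismatch between the table and the primary measure, worth correcting because the correction is simple and the tables are the plan's only sizing argument.

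**What to change.** In Protocol Tables 1 and 8-1:
- State whether 5.80 is a first-event or an all-event rate in the source database.
- Restate the serious-infection half-width for the initial-exposure ITT incidence rate on person-years that end at the first event: about ±0.99 in the first case, about ±0.96 in the second. If it is an all-event rate, replace the approximate 5.5 with the actual first-event rate.
- If ±0.93 is kept, label it as the Poisson half-width for an event rate of 5.80 over full follow-up, without crossover and without allowance for repeat infections in the same patient.

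The cost is a table edit and a slightly less favourable stated precision. No patients, data or analyses are added.
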